9. TREATMENT(S)

9.1. Appearance and content

Mesdopetam capsules, 2.5 mg, 5 mg and 7.5 mg free base equivalent: White hard HPMC capsule, coni snap size 3, colour white containing mesdopetam x $\frac{1}{2}$ L-tartrate.

Placebo capsules: White hard HPMC capsule, coni snap size 3, colour white containing starch.

9.2. Dosage and administration

The IMP (1 capsule b.i.d.) will be swallowed together with 200 mL of water in the morning and in the afternoon approximately 8 hours apart on each administration day, except for Day 56 and Day 84 when the dose will be taken in the morning at the clinic visit after trough PK sampling.

Dose run-in phase and treatment phase

Treatment allocation throughout the run-in and treatment dosing periods will be managed through the Interactive Response System (IRS) system. During the 9-day run-in phase, the IRS system will ensure all patients allocated to active dose regimen will receive 5 mg mesdopetam b.i.d, followed by the randomized dose at Visit 2 (Day 9). Patients allocated to placebo will receive placebo during the first week run-in and then continue placebo during the whole treatment period. Any dose reduction will also be managed through the IRS system to ensure that blinding is maintained.

If a patient experiences **increased parkinsonism** and/or **consistent increase in motor OFFtime**, during the treatment period from Visit 2 up to Visit 3 (i.e. Day $9 - Day 28 \pm 4 days$), the dosing can be reduced by 2.5 mg b.i.d. A dose reduction is allowed at only one occasion. A review of motor function will be performed at Visit 3.

The following tables give additional information on the two dose phases (Table 2) and the dose decrease guidance (Table 3).

Confidential	Version: 5.0	Page 39 of 74
Protocol: IRL790C005	Date: 5 Mar 2021	e

Table 2: Treatment period – dosing phases

Dose phase	Details
Dose run-in phase: Randomization Day 1. First dose taken Day 1 (evening dose) and last dose taken Day 9 (morning dose).	All patients randomized to mesdopetam will receive 5 mg b.i.d. All patients randomized to placebo will receive placebo b.i.d.
Dosing following Visit 2: First dose taken Day 9 (evening dose) and last dose taken Day 84 (morning dose/at the clinic due to PK sampling)	All patients randomized to mesdopetam will receive mesdopetam 2.5 mg, 5 mg or 7.5 mg b.i.d., as randomized. All patients randomized to placebo will continue with placebo b.i.d.

Table 3: Dose decrease guidance

Treatment period	Dose decrease guidance
Applicable for treatment from Visit 2 (Day 9) until Visit 3 (Day 28 ±4 days):	Decision to reduce the dosing is only allowed from Visit 2 (Day 9) until Visit 3 (Day 28 ± 4 days), and dose reduction is only allowed once.
	A dose reduction is only allowed if the patient experiences an increase in parkinsonism and/or a consistent increase in motor OFF-time. Increased parkinsonism is manifested as consistent increase in disability associated with parkinsonian symptoms (i.e. bradykinesia, tremor and/or rigidity).
	The following steps are permitted if the dose is decided to be reduced:
	Patients allocated to 7.5 mg b.i.d. \rightarrow dose is reduced to 5 mg b.i.d.
	Patients allocated to 5 mg b.i.d. \rightarrow dose is reduced to 2.5 mg b.i.d.
	Patients allocated to 2.5 mg b.i.d. \rightarrow dose is maintained (i.e. 2.5 mg b.i.d.).
	Patients allocated to placebo b.i.d. \rightarrow placebo b.i.d. is maintained.

Confidential	Version: 5.0	Page 40 of 74
Protocol: IRL790C005	Date: 5 Mar 2021	C

	If parkinsonism is still increased following this dose reduction, the patient and Investigator need to decide if the patient could continue with the same dose in the study (since the dose cannot be reduced further) or if the patient have to withdraw the IMP and the study. Dose reduction will be managed through the IRS system.
Patient motor function review performed at Visit 3 (Day 28 ±4 days)	This review is based on the 24-hour patient home diaries completed in the week prior to Visit 3 and the MDS-UPDRS part II assessment completed during site Visit 3. Diaries and MDS-UPDRS data are reviewed and compared to baseline.
	If there is a clinically relevant increase in OFF-time, the Investigator must determine if the increase has been consistent over time and if it is predominantly related to non-motor or motor OFF-time (according to the Investigator's clinical judgement). Evaluation of results from MDS-UPDRS part 2 (M-EDL) should be weighted in the decision. Adherence to prescribed antiparkinsonian medications should also be reviewed.
	Should a consistent increase in motor OFF-time, and/or a clinically significant worsening of mobility due to parkinsonism be assessed as likely due to the IMP, the dosing should be reduced by 2.5 mg b.i.d. at this visit. If the patient has already had a dose reduction prior to Visit 3, the dose cannot be reduced further at this visit, and the Investigator must determine whether the patient can continue in the study (i.e. continue in the study with the same dose).
	Other AEs not relating to the core symptoms of parkinsonism (such as, fatigue, headache, dystonia and other) do not qualify for dose reduction.

The reason for any dose adjustments must be recorded in the CRF. There will be no treatment with mesdopetam available after end of study participation.

Confidential	Version: 5.0	Page 41 of 74
Protocol: IRL790C005	Date: 5 Mar 2021	6

9.3. Packaging and labelling

Finished product of IMP (active drug and placebo) will be packed and labelled by Catalent Pharma Solutions.

Labels will comply with applicable Good Manufacturing Practice (GMP) requirements (EudraLex Volume 4, Good manufacturing practices, ANNEX 13, Manufacture of Investigational Medicinal Products) and applicable local regulatory guidelines. Labels will be translated into local languages.

Containers will be packed with enough IMP for the study treatment period and labelled with the appropriate information required before release and shipment.

9.4.Blinding and randomization

This is a double-blind study, thus, the study patients and the site personnel who are making the study assessments will be blinded to the study treatments of mesdopetam and placebo (capsules of mesdopetam and placebo will be of identical appearance.)

At the baseline visit (Visit 1, Day 1) patients will be randomized 1:1:1:1 to receive one of three doses of mesdopetam (2.5 mg, 5 mg or 7.5 mg) or placebo b.i.d.

During the first week (Day 1 evening dose to Day 9 morning dose) a run-in phase with either 5 mg mesdopetam or placebo b.i.d. will take place, during which all patients allocated to mesdopetam will receive 5 mg mesdopetam b.i.d. and patients allocated to placebo will receive placebo b.i.d. At Visit 2 (Day 9), patients will receive mesdopetam 2.5 mg, 5 mg or 7.5 mg or placebo b.i.d., as randomized.

Randomization will be performed via a web-based Interactive Response System (IRS), using a dynamic balancing (minimization) algorithm. Randomization will be stratified by average (based on at least two valid home diaries) of <6 daily hours or \geq 6 hours of daily ON-time with troublesome dyskinesia at baseline.

During the one-week run-in phase, the IRS system will ensure all patients allocated to mesdopetam treatment will receive 5 mg mesdopetam b.i.d, followed by the randomized dose during the treatment period. Patients allocated to placebo will receive placebo during the first week run-in and then continue placebo during the whole treatment period. Any dose reduction will also be managed through the IRS system to ensure that blinding is maintained.

Interactive Randomization System (IRS):

The IRS will manage the randomization, stratification and IMP inventory supply chain. IRS will deliver the IMP at the correct time for both new and existing patients. IRS will also support the dosing schedules and will be used to track patient activities in real time throughout study visits. Real-time web reports and alerts platform (such as email and fax) give access to compliance feedback for continuous transparency of study progress. Patient unblinding is also contained within the IRS system to allow the unblinding of patients for safety purposes within the protocol via web or phone. If emergency unblinding is required, this responsibility lies solely with the Investigator. Unblinding for other safety purposes will be managed per Sponsor outlined request. Unblinding access can be controlled within the IRS by role type allowing only the appropriate role to unblind the appropriate patient.

Confidential	Version: 5.0	Page 42 of 74
Protocol: IRL790C005	Date: 5 Mar 2021	C

Prolactin Results

Minor increases in prolactin levels may be present in participants randomized to mesdopetam. It should be noted that this elevation in prolactin is not expected to be clinically significant but could be potentially detectable if comparing Visit 5 (EOT) results to screening. For this reason, prolactin is not included in the safety lab measurements at Visit 4 and laboratory analysis results for the prolactin value at Visit 5 will be blank (i.e. not revealed to the Investigator).

PK Samples

The laboratory analysing the PK samples will have access to the randomization list; only samples taken from patients in the active group of the study will be analyzed. Results of PK analysis will not be linked to patient number until the database is locked.

Breaking the Blind

Mesdopetam and placebo (capsules of identical appearance.) will be dispensed in identical containers according to a blinded randomization scheme. Study patients, Investigators, study staff and the Sponsor will remain blinded to the randomization scheme until the blind is formally broken for all patients. For this to occur all patients must have completed the study and the study database must be locked.

Prior to database lock, a treatment assignment may be unblinded only when knowledge of the treatment received is necessary for interpreting an SAE, or essential for the medical management of the patient, or to provide critical safety information about a drug that could have implications for the ongoing conduct of the trial. Blinding codes must only be broken in emergency situations for reasons of patient safety.

Investigators will have access to the IRS system with the permissions that will enable them to selectively break the code for an individual patient. When the blinding code is broken, the reason must be fully documented and entered on the CRF.

If a patient's treatment assignment is unblinded, the Medical Monitor will be notified of the unblinding incident and the following information will be provided by the PI: date, time, patient's trial identification (number and initials), and the reason for unblinding. The patient will be withdrawn.

The identity and responsibility of those individuals at the study site who gain access to the unblinded treatment assignment must be documented. It is mandatory that all personnel who are involved in the unblinding, and who have access to the unblinded treatment assignment, maintain the confidentiality of the information and do not divulge the treatment assignment.

9.5. Treatment compliance and accountability

Patients will be instructed to bring the IMP to the study site at each applicable visit and treatment compliance will be checked. If a subject shows significant non-compliance (<80% compliance) between any two scheduled visits, Medical Monitor should be contacted for further assessment. In the event that a subject is permanently unable to return study drug to the site (i.e. drug is lost, destroyed, or discarded), the subject testimony is to be used in determining compliance.

Confidential	Version: 5.0	Page 43 of 74
Protocol: IRL790C005	Date: 5 Mar 2021	5

Unused medication and empty containers will be returned to the study site at each applicable visit. The investigators will maintain a Drug dispensing log detailing the dates and quantities of IMP received, dispensed to and used by each patient as well as IMP returned or destroyed at the end of the study. Any discrepancies between dispensed and returned IMP must be explained and documented. Products deliberately and/or accidentally destroyed by the investigator/pharmacy/Catalent or the patient must be accounted for.

9.6.Drug storage

The IMP should be stored at room temperature (not to exceed $+30^{\circ}C/+86^{\circ}F$).

Any unused IMP will be returned to Catalent or the Hospital Pharmacy for destruction. The Monitor will perform final IMP accountability reconciliation at the study end to verify that all unused IMP is adequately destroyed/returned and documented.

10.STUDY PLAN

10.1. Continuous Assessments

The following assessments will be carried out on a continuous basis and as events arise:

- AEs including SAEs
- Concomitant Medications
- IMP compliance

10.2. Screening (-56 to -10 days prior to randomization)

The following assessments will be performed and documented in all patients consented to the study to assess whether a patient meets eligibility criteria:

- Informed Consent (prior to any non-standard of care screening procedures being initiated)
- Demographics/Medical History
- Inclusion/Exclusion Criteria (screen failures to be recorded)
- Hoehn and Yahr scale
- Concomitant Medications
- Height
- Weight
- Vital Signs (including supine/standing BP)
- Physical Examination
- 12-lead ECG (triplicates separated by at least one minute)
- Haematology/Serum Chemistry/Coagulation
- Dipstick Urinalysis
- Serum Pregnancy Test (if applicable)
- MDS-UPDRS question 4.2
- 24-hour patient home diary completion training (minimum 2.5 hours). Could be done either at the screening visit or during a separate scheduled visit after receipt of the screening lab results and prior start of the baseline home diary completion period. An approved 24-hour diary trainer must perform the diary concordance session and the patient must achieve at least 75% overall diary concordance including at least one OFF interval (see section 11.2.3.1).

Confidential	Version: 5.0	Page 44 of 74
Protocol: IRL790C005	Date: 5 Mar 2021	C C

- Three 24-hour patient home diaries are handed out. Patients will be instructed to complete 24-hour home diaries for assessment of daily motor function on three days in the week before Visit 1 and bring the completed diaries to the clinic (see section 11.2.3.1. Set dates for the patients to fill in the diaries to be decided.
- MMSE
- AEs/SAEs
- General Practitioner Letter

If appropriate, the patient's General Practitioner will be informed of the patient's entry into the clinical trial.

10.3. Phone calls (-9 to -1 days prior to randomization)

Several phone calls will take place during the baseline diary completion period to remind the patient about the 24-hour home diary completion.

- Three 24-hour patient home diaries to be completed during the week (-9 to -1 days) prior Visit 1. Clinic to call the patient the working day before the first 24-hour diary completion period, as a reminder, and the working day after the last 24-hour diary completion period to encourage compliance. Screen failed patients will not complete any diaries.
- Concomitant Medications
- AEs/SAEs

10.4. Visit 1 (Baseline, Day 1)

Inclusion and Exclusion criteria will be re-assessed. Eligible patients will be randomized to either trial drug (mesdopetam) or placebo.

The following procedures and assessments will be carried out at Visit 1:

- Inclusion/Exclusion criteria
- Concomitant Medications
- Vital Signs (including supine/standing BP)*
- 12-lead ECG (single assessment)*
- Haematology/Serum Chemistry/Coagulation*
- Dipstick Urinalysis*
- Serum Pregnancy test (if applicable)
- MDS-UPDRS (all parts)
- Modified UDysRS (part 1, 3 and 4)
- Three completed 24-hour patient home diaries collected and assessed for eligibility
- Three empty 24-hour patient home diaries handed out
- CGI-S
- C-SSRS
- AEs/SAEs
- Randomization. Managed through IRS system.
- Dispense IMP. First dose of IMP to be taken in the evening at Day 1.

* If 29 days or more between Screening Visit and Visit 1 (Baseline)

Patient Information Card

Confidential	Version: 5.0	Page 45 of 74
Protocol: IRL790C005	Date: 5 Mar 2021	C C

All study patients randomized will be provided with a Patient Information Card to be carried throughout the study. The card will include the following information:

- That the carrier is participating in a clinical study
- Patient study ID
- That the carrier is potentially treated with IMP
- The name and telephone number of the Investigator
- Name and address of the Sponsor

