6. STUDY DESIGN

6.1. Overall study design and plan description

This is a multi-centre, randomized, double-blind, placebo-controlled study with the primary objective to evaluate the efficacy of 84 days' treatment with mesdopetam on ON-time without troublesome dyskinesia in patients with PD.

At the screening visit, consenting patients will be screened for eligibility according to studyspecific inclusion/exclusion criteria (see Sections 7.2 and 7.3) within 10-56 days before start of IMP administration. Diary concordance training will be performed, either during the screening visit or in the period prior to first diary completion. Patients will be instructed to selfadminister three 24-hour home diaries (before Baseline, Visit 1) for assessment of daily motor function and to bring the completed diaries to the clinic at the next visit (Baseline, Visit 1). Screen failed patients will not complete any diaries. To be eligible for randomization the patient should have completed at least two valid 24-hour home diaries.

Following baseline assessments, patients will be randomized 1:1:1:1 to receive one of three doses of mesdopetam (2.5 mg, 5 mg or 7.5 mg) or placebo b.i.d. During the first week (Day 1 evening dose to Day 9 morning dose) a dose run-in phase will take place, during which all patients allocated to mesdopetam will receive mesdopetam 5 mg b.i.d. and patients allocated to placebo b.i.d.

At Visit 2 (Day 9), patients will be dispensed mesdopetam 2.5 mg, 5 mg or 7.5 mg or placebo b.i.d., as randomized. The patients will continue the same dose for the rest of the treatment period until EOT (Day 84). Dose reductions will only be allowed if the patient manifest increased parkinsonism and/or consistent increase in motor OFF-time. The dose can only be reduced once (and only by 2.5 mg b.i.d.) (see Table 3). Dose reduction is only permitted from Visit 2 (Day 9) until Visit 3 (Day 28 \pm 4 days), where after the dosing should be kept stable until the EOT visit (Day 84).

The treatment allocation will be double-blind, i.e. it will not be disclosed to the patients, the site staff or the Sponsor. Starting on Day 1 the IMP will be self-administered by the patient at home for 12 consecutive weeks; *two oral daily doses (approximately 8 hours apart)* as adjunct treatment to the patients' regular and stable antiparkinsonian medication.

Confidential	Version: 5.0	Page 31 of 74
Protocol: IRL790C005	Date: 5 Mar 2021	C

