- 14. Drug and/or alcohol abuse.
- 15. History of severe drug allergy or hypersensitivity.
- 16. If female, is pregnant or lactating, or has a positive pregnancy test result pre-dose.
- 17. Patients unwilling to use two forms of contraception (one of which being a barrier method see Section 8.1) during the treatment period and 90 days for men and 30 days for women after last IMP dose.
- 18. Any planned major surgery within the duration of the study.
- 19. Any other condition or symptoms preventing the patient from entering the study, according to the Investigator's judgement.

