Female patients of childbearing potential must use medically acceptable methods of contraception from the time of the first administration of treatment or IMP until four weeks following administration of the last treatment or dose of IMP. A woman is considered of childbearing potential, i.e. fertile, following menarche and until becoming post-menopausal unless permanently sterile. Permanent sterilization methods include hysterectomy, bilateral salpingectomy and bilateral oophorectomy. A post-menopausal state is defined as no menses for 12 months without an alternative medical cause. A high follicle stimulating hormone (FSH) level in the postmenopausal range may be used to confirm a post-menopausal state in women not using hormonal contraception or hormonal replacement therapy. However, in the absence of 12 months of amenorthea, a single FSH measurement is insufficient.

Acceptable methods include:

- A documented placement of an IUD or IUS *and* the use of a barrier method (condom or occlusive cap (diaphragm or cervical/vault caps) used with spermicidal foam/gel/film/cream/suppository).
- Documented tubal ligation (female sterilisation). *In addition*, a barrier method (condom or occlusive cap (diaphragm or cervical/vault caps) used with spermicidal foam/gel/film/cream/suppository) should also be used.
- Oral contraceptives (combination oestrogen/progesterone containing pills), injectable progesterone or subdermal implants *and* the use of a barrier method (condom or occlusive cap (diaphragm or cervical/vault caps) used with spermicidal foam/gel/film/cream/suppository).
- True abstinence when this is in line with the preferred and usual lifestyle of the patient. *Periodic abstinence (e.g. calendar, ovulation, symptothermal, post-ovulation methods) and withdrawal are not acceptable methods of contraception.*

Confidential	Version: 5.0	Page 37 of 74
Protocol: IRL790C005	Date: 5 Mar 2021	5

Blood donation:

The patients must not donate blood or plasma during the study conduct or until three months after the final medical examination at the follow-up visit.

8.2.Concomitant medication

Permitted concomitant medication:

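### No negative pregnancy result is required at Visit 1 before randomization, dispensing and the first dose that evening

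*Protocol*

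**What the plan says.** Exclusion criterion 16 (protocol section 7.3) bars a woman who is pregnant or lactating, or who "has a positive pregnancy test result pre-dose". Section 10.4 applies the criteria again at Visit 1: "Inclusion and Exclusion criteria will be re-assessed. Eligible patients will be randomized to either trial drug (mesdopetam) or placebo". The same section lists a serum pregnancy test, then randomization, and then: "Dispense IMP. First dose of IMP to be taken in the evening at Day 1".

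The schedule footnotes 6 and 6a and section 11.2.1 fix the type of test by visit: serum hCG at screening, baseline and Visit 5, and urine hCG at Visits 3 and 4 only. In section 11.2.1, serum hCG is listed under clinical chemistry. Urine hCG is listed under dip-stick urinalysis, which is done at the clinic.

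On contraception, section 8.1 says that female patients of childbearing potential "must use medically acceptable methods of contraception from the time of the first administration of treatment or IMP". Exclusion 17 concerns willingness to use contraception during treatment and for 30 days afterwards in women.

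SAP section 6.17.8 lists the visits at which pregnancy is tested and adds no rule about when a result must be available.

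**The concern.** A serum test protects against first exposure only if it is read before the first dose. Here the sample, the randomization, the dispensing and the first capsule all fall on one day, and nothing in the text makes the later steps wait for the result.

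The Visit 1 test is also the only check that can catch a conception in the screening interval before drug is taken. If its result comes back after dosing has begun, the pregnancy is still found, but after some foetal exposure, and the patient may have to be withdrawn under section 7.4. The non-clinical summary in section 4.1.3 names a male fertility assessment in rats and reports effects on female reproductive organs in that species. It names no embryo-foetal study. That list may be incomplete, but the protocol gives no data by which to call a brief exposure harmless.

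**Working it through.** The plan gives no figure to reproduce. The check is a reading of the relevant sections side by side, with one piece of arithmetic on the visit windows.

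1. **Age of the screening test.** Section 10.2 sets screening at 56 to 10 days before randomization. A serum hCG taken at screening is therefore between 10 and 56 days old at Visit 1.

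2. **Contraception in that interval.** Section 8.1 starts the requirement for women at first administration, and exclusion 17 covers the treatment period and the 30 days after it. Neither reaches back into screening, so for up to 56 days there is neither a further test nor a contraception rule.

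3. **Where the Visit 1 sample goes.** Section 11.2.1 sends serum chemistry to a central laboratory and places hCG in the chemistry list. This is an inference, not a statement: the same sentence covers Visit 1 samples only when 29 days or more have passed since screening. Of the 10-to-56-day window, it clearly covers days 29 to 56. For days 10 to 28 no other chemistry is drawn at Visit 1, yet the hCG still is.

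4. **Turnaround.** None is stated. The nearest clue is in section 10.2, which allows diary training "during a separate scheduled visit after receipt of the screening lab results". So laboratory results are not assumed to be same-day at screening. That is suggestive for Visit 1, but does not prove it.

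5. **Is a result made a condition anywhere?**
   - Exclusion 16 names pregnancy and a positive result before dosing. It does not name a missing result.
   - Section 10.4 re-assesses the criteria but makes no laboratory result a condition.
   - Section 11.2.1 says that screening laboratory results count towards eligibility, and does not mention Visit 1 results.
   - Section 9.4 describes the interactive response system (IRS) and includes no pregnancy check before allocation.
   - By comparison, section 6.1 states the diary condition outright: "To be eligible for randomization the patient should have completed at least two valid 24-hour home diaries".

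6. **What follows if the result is late.** The latest result known at first dose is the screening one, 10 to 56 days old. The number of doses taken before the Visit 1 result arrives depends wholly on a turnaround that the documents do not give. It is none if the result arrives before the Day 1 evening dose.

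**The case against.** The strongest reply is that the protocol already says enough. Exclusion 16 bars a woman who is pregnant, whether or not a positive result is in hand, as well as one who tests positive. The criterion speaks of the time before dosing, the test is listed ahead of randomization, and only eligible patients are randomized. Unlike the Visit 1 ECG and general chemistry, the hCG is repeated for every woman to whom it applies, however recent her screening visit. Its purpose is evidently eligibility. The diary contrast is also weak: the two-diary rule is an inclusion criterion restated elsewhere, and pregnancy is an exclusion criterion enforced by the same re-assessment. Finally, the serum test may be run the same day, or the Laboratory Manual, which is not among the documents, may deal with it.

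Most of this stands. The intent is clear, and a same-day result would remove the problem. A reader might go further and infer that a site could dose a pregnant woman while following the protocol to the letter. The documents do not support that, because the first part of exclusion 16 would make her ineligible. A reader might also want to put a capsule count or milligram dose on the exposure. That would rest on an invented turnaround.

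What the reply does not answer is the practical point: an investigator cannot apply either part of exclusion 16 to a pregnancy not yet known. Section 11.2.5.1 assigns the Laboratory Manual specimen preparation, handling, storage and shipment; eligibility is not mentioned.

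**Conclusion.** The point holds as a gap in procedure, not in intent. The plan means to keep pregnant women off study drug, but does not require the one test that could show a new pregnancy to be read first. The gap matters only if the Visit 1 serum result is not available the same day. That is probable if the sample goes to the central laboratory, but the documents do not establish it.

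The size is small. It concerns women of childbearing potential in a population aged 30 to 79; their number is not given and is assumed to be low. Exposure would end once the serum result was reported and acted on, and its extent cannot be derived. No estimate, test or analysis set is affected in any way that matters. This is a cheap improvement on a minor safety point.

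**What to change.** In section 10.4, schedule footnotes 6 and 6a, and section 11.2.1, require for women of childbearing potential a recorded negative pregnancy result at Visit 1 before IRS randomization and dispensing. Either a urine hCG read at the site, as already done at Visits 3 and 4, or a serum result reported the same day would meet it.

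Keep the serum test as confirmation. A positive urine test holds randomization until serum settles it; a later positive serum result stops study drug. The second rule is worth writing down, because section 7.4 now gives the investigator the right to withdraw such a patient but does not oblige it. A pregnancy that urine misses and serum detects could still be exposed briefly, so the residual risk is reduced, not removed.

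The cost is one schedule entry, a sentence or two, and one urine kit per woman of childbearing potential. The downside is a delay to randomization after a false-positive urine test. SAP section 4 shows recruitment was well advanced when it was written, so the change would reach only patients still to be randomized and any later protocol.
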